7.7. Replacement of Subjects

Enrolled subjects that do not complete all visits will be replaced to ensure that 30 evaluable subjects complete the study.

7.8. Criteria for Study Termination

This study may be terminated prematurely in whole or in part due to a change in the benefit/risk profile for ATI-502 Topical Solution such that continuation of the study would not be justified on medical or ethical grounds. This determination may be made by the Study Investigators in conjunction with the Sponsor, or by the Institutional Review Board (IRB) or the U.S. Food and Drug Administration (FDA). The Sponsor may also elect to terminate the study if enrollment is sufficiently slow to prevent the completion of the study in an acceptable timeframe, or if ATI-502 development is discontinued.

If the study is terminated prematurely, the Sponsor will notify the Study Investigators and the FDA. The Investigator must promptly notify all enrolled subjects and the IRB of study termination.

8. STUDY PROCEDURES

[Table 2](#) provides a summary of all study specific assessments that are required for this protocol.

Table 2: Schedule of Assessments

	Screening	Baseline	Treatment			Post Treatment Safety Follow up Visit ¹³
	Visit 1	Visit 2	Visit 3	Visit 4	Visit 5	Visit 6
Week		0	1	2	4	8
Treatment Day	-14 to 0	1	8	15	29	56
Treatment Window(days)	N/A	N/A	± 3	± 3	± 3	+7
Informed consent ¹	▲					
Inclusion/exclusion criteria	▲	▲				
Physical exam ²	▲					▲
Demographics & Medical History	▲					
Vital Signs ³	▲	▲	▲	▲	▲	▲
Fitzpatrick Skin Type	▲					
Atopic Dermatitis History ⁴	▲					
Clinical Chemistry and CBC ⁵	▲	▲	▲	▲	▲	▲
QuantiFERON Gold ⁶	▲					
Virology [HepB (HBsAg), HCV (antibody), HIV (antibody)]	▲ ⁷					
Serum Pregnancy	▲					
Urine Pregnancy		▲				▲
ECG	▲		▲	▲	▲	▲
Physician's Global Assessment (PGA)	▲	▲	▲	▲	▲	▲
Body Surface Areas Assessment	▲	▲	▲	▲	▲	▲
Identification of AD Treatment Area	▲	▲				
Eczema Area and Severity Index (EASI)	▲	▲	▲	▲	▲	▲
Subjects Pruritis Assessment (SPA)		▲	▲	▲	▲	▲
Signs of Atopic Dermatitis (SAD)		▲	▲	▲	▲	▲
Standardized Photography ⁸	▲	▲	▲	▲	▲	▲
Dispensing of study medication ⁹		▲	▲	▲		
Treatment with ATI-502		▲ ¹⁰	▲	▲	▲	
Subject Instructions ¹¹	▲	▲	▲	▲	▲	
Concomitant medications/therapies	▲	▲	▲	▲	▲	▲
Adverse Events ¹²	▲	▲	▲	▲	▲	▲

¹ A written, signed ICF must be obtained from each subject prior to performing any study related procedure

² A physical exam includes: general appearance, examination of head, eyes, ears, nose and throat, extremities, respiratory, cardiovascular, abdominal, neurological, musculoskeletal, lymphatic and skin assessment.

³ Vital signs include: oral or ear temperature, blood pressure, heart rate, respiration rate (height and weight at baseline only).

⁴ Prior therapies or treatments a subject received to treat AD must be documented for each subject.

⁵ Serum chemistry panel to include: albumin, alkaline phosphatase, ALT, AST, BUN, bicarbonate, calcium, chloride, creatinine, glucose, lactate dehydrogenase (LDH), phosphorus, potassium, sodium, total bilirubin, total protein, uric acid, total cholesterol, LDL, HDL triglycerides, and complete blood count including differential.

⁶ All subjects must have a blood sample drawn to test for the tuberculosis virus (QuantiFERON Gold). The blood sample will be sent to a central laboratory for analysis and results must be received prior to enrolling the subject.

⁷ All subjects will be required to have virology testing for HepB (HBsAG), HCV(antibody), and HIV (antibody). If a subject demonstrates to have serological evidence HepB (HBsAG), HCV (antibody) or HIV (antibody), the subject will not be allowed to enroll to the study.

⁸ Canfield staff will review all photographs within 2 days of the photographs being submitted. If a re-take is required, Canfield will notify the site and the re-take photographs will need to be performed within 7 days of the visit. Prior to enrollment to the study, each subject's Visit 1 photos will be reviewed by a panel of board certified dermatologists to ensure that the subject's target areas for treatment meet the study entry criteria. In cases where the photographs do not properly characterize the disease (due to flashback and whitening on the photographs) the subjects will be allowed to enroll to the study based upon the Principal Investigator's clinical assessment of the subject.

⁹ At visit 2, following confirmation that the subject is approved for enrollment to the study, the site will weigh and dispense supplies of ATI-502 study medication and disposable droppers to the subject for at home application of the study medication.

¹⁰ All subjects will have their first application of study medication applied in the clinic during Visit 2. Subjects will continue to apply ATI-502 Topical Solution, 0.46% to all target areas twice a day for 4 weeks (Day 28) unless the subject meets the criteria for treatment interruption. If new areas of AD develop, subjects will be allowed to treat these areas with the ATI-502 study medication.

¹¹ Sites will be required to review with each subject the proper application of the study medication and remind that they must refrain from exercise that may cause excessive sweating, bathing or swimming for a period of 6 hours after the application of study medication. Subjects are also to be reminded that they may not apply moisturizers, emollients, or sunscreen to target AD areas during protocol treatment.

¹² All non-serious AEs will be collected from the time of first study medication application until the final study visit. Serious AEs will be collected from the time of consent through the final study visit.

¹³ A final safety follow up visit will be conducted at week 8 (Visit 6). For those subjects that discontinue the study early, they must return to the clinic 4 weeks following the last study medication application for a final safety visit.

9. SELECTION AND WITHDRAWAL OF SUBJECTS

9.1. Subject Inclusion Criteria

Subjects must meet the following criteria to be eligible for participation in the study:

1. Able to comprehend and willing to sign an Informed Consent Form (ICF).
2. Male or non-pregnant, non-nursing female subjects ≥ 18 years old at the time of informed consent.
3. Subject must have diagnosis of AD according to the Hanifin and Rajka criteria.
4. Subject must have a diagnosis of moderate (PGA =3) or severe (PGA=4) AD for a period of ≥ 6 months prior to the first dose of study medication (Visit 2).
5. Subject Visit 1 photographs are approved for enrollment by the dermatology review panel.
6. Body surface area involvement must be between 2-20% (excluding scalp, face, palms of hands, soles of feet, groin and genitalia).
7. Subject must have an absolute neutrophil count (ANC) and a platelet count within normal limits
8. Subject must be willing to refrain from washing area of treatment or swimming for 6 hours after each treatment application with ATI-502.
9. Subjects must be willing to refrain from excess of sun exposure.
10. Subject is willing and able to follow all study instructions and be willing to attend all study visits.
11. Subject must refrain from participating in strenuous exercise that would cause profuse sweating for a period of 6 hours after each treatment application with ATI-502.
12. Subject must refrain from using moisturizers, emollients, and sunscreen on target AD treatment area for the duration of protocol therapy.
13. Be in good general health and free of any known disease state or physical condition which, in the investigator's opinion, might impair evaluation of the subject or which might expose the subject to an unacceptable risk by study participation.
14. If a woman of childbearing potential (WOCBP), must have a negative serum pregnancy test at Screening (Visit 1) and a negative urine pregnancy test at Baseline (Visit 2) and agree to: use a highly effective method of birth control for the duration of the study; not be planning a pregnancy during the study duration and use contraception for 30 days after last application of study medication.
15. Sexually active male subjects must agree to use a barrier method of contraception from the first application of study medication to at least 30 days after the last application of study medication.

9.2. Subject Exclusion Criteria

1. Subject has any signs or symptoms associated with AD therapy (e.g., history of anaphylaxis, hypersensitivity reactions, skin atrophy, striae, pigmentary changes) which, in the investigator's opinion, might impair evaluation of the AD or which exposes the subject to unacceptable risk by study participation.
2. Subjects unable to complete the following required washout periods:
 - Phototherapy within 4 weeks prior to Visit 1.
 - Systemic immunosuppressant or immunomodulatory therapy (e.g. etanercept, alefacept, infliximab, methotrexate) within 16 weeks prior to Visit 1.
 - JAK inhibitors (systemic and topical) within 4 weeks prior to Visit 1.
 - Systemic corticosteroids (intranasal and inhaled corticosteroids are allowed) within 4 weeks prior to Visit 1.
 - Cytostatic agents within 4 weeks prior to Visit 1.
 - Crisaborole within 2 weeks prior to Visit 1.
 - Dupilumab or other monoclonal antibody within 3 months prior to Visit 1.
 - Systemic antibiotics with 2 weeks prior to Visit 1.
 - Topical treatments for atopic dermatitis (corticosteroids, calcineurin inhibitors, topical H1 and H2 antihistamines, topical antimicrobials, and other medicated topical agents) within 1 week prior to Visit 1.
 - Live attenuated vaccine treatment within 12 weeks prior to Visit 1.
3. Use of prescription moisturizers within 7 days of Visit 1.
4. Subject has used any emollients/moisturizers on the planned treatment area (s) within 4 hours of Visit 1.
5. Subject has clinically infected AD.
6. Subject is currently using an oral H1 antihistamines (e.g. diphenhydramine, terfenadine) UNLESS the subject is on a stable dose for at least 14 days prior to Visit 1.
7. Clinically significant laboratory abnormalities at Visit 1 that, in the opinion of the Investigator, would make the subject a poor candidate for the study
8. History of, or current, severe, progressive or uncontrolled renal, hepatic, gastrointestinal, pulmonary, cardiovascular, genitourinary (renal disease) or hematological disease, neurologic or cerebral disorders, infectious disease or coagulation disorders that, as determined by the Investigator, would preclude participation in and completion of study assessments.
9. History of, current or suspected systemic or cutaneous malignancy and /or lymphoproliferative disease, other than subjects with: a history of adequately treated and well healed and completely cleared non-melanoma skin cancers (basal or squamous cell carcinoma) treated successfully at least 1 year prior to study entry with no evidence of disease.

10. Evidence of active or latent bacterial (including tuberculosis) or viral infections at the time of enrollment or history of incompletely treated or untreated tuberculosis. Subjects who have completed therapy for latent tuberculosis may participate.
11. History of a serious local infection (*e.g.*, cellulitis, abscess) or systemic infection including but not limited to a history of treated infection (*e.g.*, pneumonia, septicemia) within 3 months prior to Visit 2. Subjects on an antibiotic for a non-serious, acute local infection must complete the course prior to enrollment into the study.
12. Positive serological test for HIV(antibody), HCV (antibody), or HepB (HBsAg).
13. Subjects with herpes zoster or cytomegalovirus (CMV) that resolved less than 2 months before study enrollment. Subjects with a history of frequent outbreaks of Herpes Simplex Virus (defined as 4 or more outbreaks a year).
14. Screening ECG findings of:
 - a. QTcF >450msec for males or >470msec for females (use of the ECG algorithm is acceptable for this purpose)
 - b. Resting heart rate \leq 45 or Heart Rate \geq 100 beats/minutes if considered to be caused by a clinically significant pathology. The investigator may enter a patient with a HR outside of these values if considered to have no clinical significance.
 - c. Rhythm disturbance other than sinus arrhythmia or ectopic supraventricular rhythm (ectopic atrial rhythm)
 - d. Conduction disturbance including PR >240msec, pre-excitation (delta wave and PR <120msec), second degree or higher AV block
 - e. Acute or chronic signs of ischemia
 - f. Left Bundle Branch Block
 - g. Prior myocardial infarction
15. Subject has participated in an investigational drug trial within 30 days prior to Visit 1.

9.3. Subject Withdrawal Criteria

Subjects will be informed that they are free to withdraw from the study at any time and for any reason. The investigator may remove a subject from the study if, in the investigator's opinion, it is not in the best interest of the subject to continue the study. Examples of other reasons subjects may be discontinued from the study are: a change in compliance with an inclusion or exclusion criteria, occurrence of AEs, occurrence of pregnancy, use of a prohibited therapy or subject is unwilling or refuses to continue with the protocol defined procedures, treatments and/or study visits and/or subject withdraws consent.

The date the subject is withdrawn from the study and the reason for discontinuation must be recorded in the subject's electronic case report forms (eCRFs). All withdrawn subjects will be required to complete one last safety follow up visit approximately 30 days after last study medication application. If the subject withdraws their consent to have this visit completed this needs to be appropriately documented in the subject's source notes and on the subject's eCRF.

Subjects will be permanently discontinued from the study in the event of any of the following:

- Severe infection requiring parenteral antimicrobial therapy or hospitalization
- Symptomatic herpes zoster

- Malignancy – except for non-melanoma skin cancer (SCC or BCC) not in or near the treatment area
- Anaphylactic or severe allergic reaction
- WBC Count: $< 1 \times 10^9/L$ or second occurrence of $< 2 \times 10^9/L$
- ANC: $< 0.5 \times 10^9/L$ or second occurrence of $< 1 \times 10^9/L$
- Lymphocyte count: $< 0.3 \times 10^9/L$ or second occurrence of $< 0.5 \times 10^9/L$
- Platelet count: $< 50 \times 10^9/L$ or second event of $< 75 \times 10^9/L$ - in each case, value should be confirmed by retesting before treatment discontinuation
- Hemoglobin: $< 6.5 \text{ g/dL}$ or second occurrence of $< 8 \text{ g/dL}$ - in each case, value should be confirmed by retesting before treatment discontinuation
- AST or ALT:
 - $> 5 \times \text{ULN}$ persisting for 2-weeks of study medication interruption or second event of $> 5 \times \text{ULN}$
 - $3 \times \text{ULN}$ with total bilirubin $> 2 \times \text{ULN}$ or symptoms of hepatocellular injury [fatigue, nausea, vomiting, right upper quadrant pain or tenderness, fever, rash and/ or eosinophilia ($> 5\%$)].
- Any subject who develops any of the following ECG findings during the active treatment phase will be instructed to stop study medication and will be withdrawn from the study:
 - Clinically significant rhythm disturbance other than sinus rhythm or ectopic supraventricular rhythm (ectopic atrial rhythm)
 - Clinically significant conduction disturbance including PR $> 240 \text{ msec}$, pre-excitation (delta wave and PR $< 120 \text{ msec}$), second degree or higher AV block
 - New finding of QRS $> 120 \text{ ms}$ (if not present at screen. For example, subjects with Right Bundle Branch Block at screening would not need to be withdrawn from the study if their subsequent ECGs remained unchanged).
 - Evidence of QT-interval prolongation, defined as an increase in the QTcF interval $> 60 \text{ ms}$ from Visit 1
 - Acute signs of ischemia or infarction
 - Any ECG abnormality which may, in the opinion of the investigator, represent a new medical issue of concern

A subject that experiences any of the above events must be discontinued from study medication treatment, the site staff must inform the Aclaris medical monitor of the event, and the site staff must perform protocol-required procedures for trial discontinuation and follow-up.

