11.3. Study Medication Interruption

Treatment with ATI-502 Topical Solution, 0.46% should be temporarily interrupted in the event of severe adverse events considered related to ATI-502 Topical Solution, 0.46%, or in the event of one or more of the abnormal laboratory values in [Table 4](#).

Table 4: Study Medication Interruption Criteria

Laboratory Test	Hold Study Medication if:	Resume Study Medication if:
WBC count	$< 2 \times 10^9/L$	$\geq 2.5 \times 10^9/L$
ANC	$< 1 \times 10^9/L$	$\geq 1.5 \times 10^9/L$
Lymphocyte count	$< 0.5 \times 10^9/L$	$\geq 0.75 \times 10^9/L$
Platelet count	$< 75 \times 10^9/L$	$\geq 100 \times 10^9/L$

Hemoglobin	< 8 g/dL or a decrease > 2g/dL	≥ 10 g/dL
AST or ALT	> 3 x ULN	< 2 x ULN or within 20% of Baseline values
Serum creatinine	>2 x ULN	<1.5 x ULN or within 10% of Baseline value

If a subject has one or more of the abnormal laboratory values noted in [Table 4](#), the investigator or designee upon receipt and review of the central laboratory report should instruct the subject to hold study medication applications. The investigator or designee should ask the subject about symptoms, concomitant illnesses and medications and repeat the test(s) as soon as possible. The Medical Monitor must be notified of dose interruptions due to SAEs considered related to study medication or laboratory abnormalities noted in [Table 4](#).

If the retest confirms the abnormal laboratory value, then the study medication should continue to be held followed by repeat testing once a week or sooner at the discretion of the investigator. The subject should be followed until the laboratory abnormality(s) returns to normal or to baseline values.

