13.3.4. Procedures for reporting adverse events

At each post-enrollment visit, the investigator will question the subject to elicit AEs using a non-directive question such as “Has there been any change in your health since the previous study visit?” If appropriate, based on the subject’s response to non-directed questioning to elicit AEs, the investigator will follow-up with directed questions and appropriate evaluations.

Any AE noted during the reporting period must be reported in the source documents and on the appropriate AE eCRF. AEs that are defined as “Not Related” to the study medications will be followed until they are resolved or until the subject’s last study visit. AEs that are defined as “Related” to the study medications will be followed until they are resolved or, if not resolved at the subject’s last study visit, until in the opinion of the investigator, the AE reaches a clinically stable outcome with or without sequelae.

Should a pregnancy occur, it must be reported and recorded on Aclaris pregnancy form. Pregnancy in itself is not regarded as an AE unless there is a suspicion that an investigational product may have interfered with the effectiveness of a contraceptive medication.

The outcome of all pregnancies (spontaneous miscarriage, elective termination, normal birth or congenital abnormality) must be followed up and documented even if the patient was discontinued from the study.

All reports of congenital abnormalities/birth defects are SAEs. Spontaneous miscarriages should also be reported and handled as SAEs. Elective abortions without complications should not be handled as AEs.

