13.3.5. Procedure for reporting a serious adverse event

Upon becoming aware of a SAE occurring during the AE reporting period, whether or not related to the study medications, the investigator must:

1. Take the appropriate medical action to ensure the subject’s safety.
2. Immediately inform the Safety Monitor of the SAE by email, ensuring that the subject information is deidentified (only subject initials and subject number) to: **ProPharma, Email: [contact]**.
3. Print a copy of the email confirmation from ProPharma and place in the study file.
4. Within 24-hours complete, as fully as possible, an AE eCRF and an SAE form; e-mail the forms and any other relevant information (e.g., concomitant medication eCRF, medical history eCRF, laboratory test results) to ProPharma.
5. Monitor and document the progress of the SAE until it resolves or, if not resolved after the subject’s last study visit, until in the opinion of the investigator the AE reaches a clinically stable outcome with or without sequelae AND the investigator and Aclaris

Therapeutics, Inc. Safety and Medical Monitor agree that the SAE is satisfactorily resolved.

6. Inform the Aclaris Therapeutics, Inc. Safety Monitor of SAE updates, via telephone, followed by an SAE form update sent by e-mail.
7. Comply with the appropriate regulatory requirements and Aclaris Therapeutics, Inc. instructions regarding reporting of the SAE to the responsible Institutional Review Board (IRB) or Ethics Committee (EC).

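### After an ECG stop under Protocol 9.3 no repeat ECG is dated before the final safety visit, and a subject stopped before Visit 5 is left out of the Week 4 EASI and PGA responder percentages

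*Protocol*

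**What the plan says.** **Stopping.** Protocol 9.3 removes the subject from the study, not only from the drug: "Subjects will be permanently discontinued from the study in the event of any of the following". For the listed ECG findings during active treatment, the subject "will be instructed to stop study medication and will be withdrawn from the study". The medical monitor must be told, and "the site staff must perform protocol-required procedures for trial discontinuation and follow-up". No section lists those procedures, and the schedule (Protocol Table 2) has no early-termination column.

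**After the stop.** One visit is dated. Protocol 9.3 says "All withdrawn subjects will be required to complete one last safety follow up visit approximately 30 days after last study medication application"; footnote 13 of Table 2 says "For those subjects that discontinue the study early, they must return to the clinic 4 weeks following the last study medication application". Protocol 13.1.4 schedules ECGs at Visits 1, 3, 4, 5 and 6 only.

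**Other follow-up.** For laboratory values beyond a Table 4 limit, Protocol 11.3 asks for a retest as soon as possible. If the value is confirmed, the drug stays on hold, "followed by repeat testing once a week or sooner at the discretion of the investigator", and the subject is followed to normal or baseline values. Under 13.3.4, a related AE still open at the last visit is followed "until in the opinion of the investigator, the AE reaches a clinically stable outcome with or without sequelae". For serious events, 13.3.5 tells the investigator to "Monitor and document the progress of the SAE until it resolves" or is stable.

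**Analysis.** SAP 4.1.1 puts every dosed subject in the Efficacy Population. SAP 4.2 then limits post-baseline analyses to non-missing values at the visit named on the CRF. SAP 4.2.1 (EASI) and 4.2.3 (PGA) tabulate responder percentages by visit without stating a denominator. The only sensitivity set, Per-Protocol, requires completion of Visit 6. Protocol 7.7 replaces subjects who do not complete all visits.

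**The concern.** Safety is the primary outcome, and the ECG rules are among the reasons for which a subject must leave the study. When one of them fires, the reader of the results will want to know whether the finding resolved once the drug was stopped, and how soon. The protocol builds that check in for laboratory values but not for ECGs.

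On the efficacy side, the subjects who leave early are those with a safety problem. If they also respond less often, a Week 4 percentage calculated only on those still present is too favourable. Replacement restores the observed number to 30, so the table itself would show no sign of the loss.

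**Working it through.** **1. Which stops already have dated follow-up.** The 9.3 limits for white cells, neutrophils, lymphocytes, platelets, hemoglobin and ALT/AST lie at or beyond the Table 4 hold limits. For example, ANC below 0.5, or a second value below 1, against a hold below 1 (all × 10⁹/L). Such stops therefore come under the 11.3 retest, and 9.3 itself adds a confirmatory retest for platelets and hemoglobin. Table 4 contains no ECG item.

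**2. Whether AE follow-up closes the ECG gap.** Under 13.1.4, an abnormal ECG after the first dose becomes an AE only if the investigator considers it clinically significant. In 9.3 the rhythm and conduction stops carry that qualifier. The stops for a new QRS above 120 ms and for a QTcF increase above 60 ms do not. A subject can therefore be withdrawn for one of these without an AE being recorded, and 13.3.4 then has nothing to follow. Where 13.3.4 or 13.3.5 does apply, neither dates an ECG.

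**3. Length of the gap.** Next dated ECG = day of last application + 28 (footnote 13) or + 30 (9.3). This takes the last application as the day of the abnormal ECG.

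| ECG stop at | Next dated ECG | Repeat at +7 to +14 days |
|---|---|---|
| Visit 3, Day 8 | Day 36 to 38 | Day 15 to 22 |
| Visit 4, Day 15 | Day 43 to 45 | Day 22 to 29 |

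The gain is 36 − 22 = 14 to 38 − 15 = 23 days for Visit 3, and 43 − 29 = 14 to 45 − 22 = 23 days for Visit 4. A subject who stays on the drug is rechecked after 7 days (Visit 3 to 4) or 14 days (Visit 4 to 5).

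**4. Week 4 responder percentage.** The plan has no figure to reproduce: SAP 4.4 gives 30 subjects with no formal basis, and neither document gives a response or dropout rate. Assume r responders among 30 subjects observed at Week 4 (after replacement) and k stopped subjects. The observed-case rate is r/30. The all-dosed rate with missing counted as non-response is r/(30 + k).

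For r = 12:

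- Observed: 12/30 = 40.0%.
- k = 1: 12/31 = 38.7%, a difference of 1.3 points.
- k = 2: 12/32 = 37.5%, a difference of 2.5 points.
- k = 3: 12/33 = 36.4%, a difference of 3.6 points.

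The standard error of 12/30 is √(0.4 × 0.6/30) = 0.089, or 8.9 points. The differences for k = 1 and k = 3 are 0.0129/0.0894 = 0.14 and 0.0364/0.0894 = 0.41 of it.

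For k = 1 to 3, the range is 0.6 to 1.8 points with r = 6 (6/30 − 6/31; 6/30 − 6/33) and 1.9 to 5.5 points with r = 18 (18/30 − 18/31; 18/30 − 18/33).

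These are the largest upward biases for the given counts. The direction is not certain: if all three stopped subjects would have responded, the rate would be 15/33 = 45.5%, and the observed 40.0% would be too low.

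**5. Whether the Per-Protocol set shows this.** It does not. It narrows towards completers and uses the same observed-data rule. Even if an early final visit were recorded as Visit 6, the subject would still have no Week 4 value. EASI also has a summary of response at any post-baseline visit, which can include the subject; PGA has none.

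**The case against.** The best case for the plan is that follow-up is not absent. An ECG finding considered clinically significant is an AE, a related AE is followed until it is stable, infarction would fall under the serious-event rules, and the medical monitor is told of every such stop. Leaving the timing of a repeat ECG to the investigator is a legitimate choice, and the documents contain no source for an interval of 1 to 2 weeks. ECGs are also taken at visits that collect vital signs, laboratory tests, PGA and EASI, so an ECG stop normally has that visit's data. All of this stands. It does not supply a date, and it does not reach a QRS or QTcF stop that is not recorded as an AE. The interval proposed here simply matches the 7- and 14-day visit spacing.

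On the percentages, Protocol 14.1 says that binary data are shown with the overall number of subjects, and all dosed subjects belong to the Efficacy Population. One could read the denominator as everyone dosed. The denominator is indeed unstated, but the specific rule in SAP 4.2 points to subjects with a value at that visit.

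A reader might also infer that any stop between visits leaves the subject with no required assessment. The documents do not support that. Laboratory stops are retested, serious clinical events are followed to resolution or stability with forms and relevant results due within 24 hours, and the final safety visit is required. What remains is narrower: a clinical stop between visits, such as uncomplicated herpes zoster, has no vital signs or ECG required at the time.

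**Conclusion.** The point holds in two limited parts.

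- **ECG follow-up.** After an ECG stop at Visit 3 or 4, no ECG is dated for 28 to 30 days, and AE follow-up need not cover the QRS and QTcF stops. This rests on the text alone, with the last application taken as the visit day.
- **Week 4 responder rates.** Under the observed-data rule, subjects stopped before Visit 5 are absent from the EASI-75, EASI-50 and PGA percentages. The possible upward bias is 1.3 to 3.6 points for 12 of 30 with one to three stops, under half a standard error. The counts are assumed, and the bias is zero if stopped subjects would have responded at the observed rate.

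Two stronger conclusions do not follow. Stopped subjects are not lost from the safety results: the AE tables, the ECG worst-shift table, the hepatobiliary and renal counts and the disposition summary can all include them. Nor do the documents show that the response rate is inflated, since nothing in them says that stopped subjects respond less. Efficacy is secondary and there are no inferential statistics, so no test or decision rule changes. This is a cheap improvement, not a flaw in the trial's conclusions.

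**What to change.** 1. **Protocol 9.3 and Table 2 footnote 13.** Require a repeat ECG about 1 to 2 weeks after an ECG stop, recorded as unscheduled. For a non-laboratory clinical stop between visits, collect vital signs and an ECG at an early-termination contact where clinically feasible, so that a hospitalised subject is not in breach. The stopping criteria, the final safety visit and 7.7 stay as they are.
2. **SAP 4.2.1 (EASI) and 4.2.3 (PGA).** Next to the observed-case rate, report the Week 4 responder rate with all dosed subjects as the denominator and missing values counted as non-response. Footnote how many were stopped for an AE or a 9.3 criterion and how many were missing for other reasons.

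How the early final visit is labelled also deserves a line, as clarification only; the CRF or the separate data-handling document named in SAP 4.3 may already settle it.

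The cost is amendment wording, one extra visit for a few subjects, one more row in two tables, and a slightly lower second response rate beside the first.
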